intervention as well as pre-post multimodal evaluation. As for the quantification of changes in amyloid load, we will compare individual *relative standard uptake values* (SUVR) before and after tACS, according to established threshold values. PET Amyloid levels across brain regions will be quantified using standard uptake values normalized to uptake in the cerebellum (SUVR; (Lopresti et al., 2005)). Studies have suggested that the test-retest reliability of amyloid-PET measurement is high, with an intraclass correlation of 0.99, and a relative measurement error of 3% (C. R. Jack et al., 2013). Subjects will be defined as amyloid positive if the global (across all regions) cortical to cerebellar SUV ratio is greater than or equal to 1.6 (Clifford R. Jack et al., 2008). The annual rate of change in the global and regional amyloid ratio varies as a function of patient clinical status and baseline SUVR, but is generally either nonsignificant or small but positive, typically on the order of 0.05 units/yr, and asymptotes in patients with cognitive deficits and high amyloid levels (C. R. Jack et al., 2013; Clifford R. Jack et al., 2009; Villain et al., 2012; Villemagne et al., 2013), suggesting that major changes are unlikely over the short time period between baseline and post-intervention testing. Furthermore, significant decreases in amyloid (> 0.05 units/yr) are rare, particularly in patients with MCI/AD (C. R. Jack et al., 2013), suggesting that decreases above this magnitude would represent a reliable measure of tACS effect. Changes in SUVR will be evaluated by looking at individual trajectories of amyloid change (i.e. decrease in amyloid load or slowing of amyloid build-up) exceeding the threshold.

Data Analysis:

Changes in EEG metrics (e.g. gamma spectral power), amyloid beta levels, clinical and cognitive scores, as well as brain plasticity levels, will be measured using paired-sample t-test statistics, by applying a p.value < 0.05 . Details about computation EEG-based measures are described below.

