- Current or past history of any neurological disorder other than dementia, such as epilepsy, stroke (cortical stroke), progressive neurologic disease (e.g. multiple sclerosis) or intracranial brain lesions; and history of previous neurosurgery or head trauma that resulted in residual neurologic impairment.
 - Non-cortical disease such as confluent white matter changes (including lacunar infarcts < 1 cm) and asymptomatic, subacute, cerebellar infarcts may be included upon review of a medically responsible neurologist.
- Past or current history of major depression, bipolar disorder or psychotic disorders, or any other major psychiatric condition.
- Contraindication for undergoing MRI or receiving TMS or tACS,
- History of fainting spells of unknown or undetermined etiology that might constitute seizures.
- History of seizures, diagnosis of epilepsy, history of abnormal (epileptiform) EEG or immediate (1st degree relative) family history of epilepsy; with the exception of a single seizure of benign etiology (e.g. febrile seizure) in the judgment of the investigator.
- Chronic (particularly) uncontrolled medical conditions that may cause a medical emergency in case of a provoked seizure (cardiac malformation, cardiac dysrhythmia, asthma, etc.).
- Metal implants (excluding dental fillings) or devices such as pacemaker, medication pump, nerve stimulator, TENS unit, ventriculo-peritoneal shunt, cochlear implant, unless cleared by the study MD.
- Substance abuse or dependence within the past six months.
- Medications will be reviewed by the responsible MD and a decision about inclusion will be made

based on the following: The patient's past medical history, drug dose, history of recent medication changes or duration of treatment, and combination of CNS active drugs.

- All female participants that are pre-menopausal will be required to have a pregnancy test; any participant who is pregnant will not be enrolled in the study.
- Subjects who, in the investigator's opinion, might not be suitable for the study
- A hair style or head dress that prevents electrode contact with the scalp or would interfere with the stimulation (for example: thick braids, hair weave, afro, wig)

STUDY VISIT SCHEDULE																	
Procedures	Screening ^A (Day 1-4)			Daily Visits (Day 5-14)										Follow-up ^B (Day 15-18)			Telephone Follow-up (1 mo. and 3 mo. post study)
	1	2	3	1	2	3	4	5	6	7	8	9	10	1	2	3	
Neurological exam	X*																
Demographic Review	X*																

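### Cerebellar infarcts are admissible while cerebellar uptake is the SUVR denominator, with no stated check or masking; a lesion that evolves between scans could shift SUVR by about 3%, enough to mimic or hide a 0.05 fall

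*Combined protocol and SAP*

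**What the plan says.** Section B3.C (Subject Selection, Exclusion Criteria) excludes intracranial lesions in general, then opens an exception: "asymptomatic, subacute, cerebellar infarcts may be included upon review of a medically responsible neurologist". The 1 cm limit in the same sub-bullet attaches to lacunar infarcts. No size is given for a cerebellar infarct, and the review is not tied to PET quantification.

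Section B3.B (Statistical Considerations, Sample Size Justification) sets the amyloid measure: "PET Amyloid levels across brain regions will be quantified using standard uptake values normalized to uptake in the cerebellum". Positivity requires that the global "cortical to cerebellar SUV ratio is greater than or equal to 1.6". On change, it says that "significant decreases in amyloid (> 0.05 units/yr) are rare", "suggesting that decreases above this magnitude would represent a reliable measure of tACS effect", and it plans to judge individual trajectories against that threshold. The 0.05 is quoted as a yearly rate but is used as a size of fall, and I read it that way. The same section cites "a relative measurement error of 3" per cent for the PET measure. Under Data Analysis, amyloid change is also tested with a paired t-test, "by applying a p.value < 0.05".

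Neither section mentions masking a lesion, checking the reference region, using another reference region, or a sensitivity analysis. There is no control arm (B3.A, Overview).

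**The concern.** SUVR is a ratio, so a change in its denominator moves it as surely as a change in cortical amyloid. The protocol admits lesions in the one structure that it relies on as a stable denominator, and describes them as subacute, which makes change between two scans plausible. Because every regional value shares the denominator, a shift would move all regions by the same proportion, including the stimulated target.

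Two results are exposed. The first is the change used for Aim 2, where a denominator shift could be counted as a response or could conceal one. The second is the baseline value compared with 1.6. B3.B expects 5/6 completers, so one affected patient would be 1/6 to 1/5 (17% to 20%) of the Aim 2 data. With no control arm, nothing in the design would separate the artefact from an effect.

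**Working it through.** The plan derives no figure that depends on the reference region, so there is nothing of its own to reproduce.

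**Inputs from B3.B:** positivity 1.6; notable fall 0.05; measurement error 3%; 5/6 completers.

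**Assumptions (the documents give none of these):** an infarct lowers tracer uptake; it fills a share f of the reference region with a fractional uptake deficit d; uptake may recover by the second scan. The true SUVR, T, is held constant.

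**1. Denominator rise that reads as a 0.05 fall.** From an observed baseline S, the rise is S/(S − 0.05) − 1.
- S = 1.6: 1.6/1.55 − 1 = 3.2%
- S = 2.0: 2.0/1.95 − 1 = 2.6%

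**2. Lesion needed.** Observed SUVR = T/(1 − f·d). With full recovery the spurious fall is T/(1 − f·d) − T, which exceeds 0.05 when f·d > 0.05/(T + 0.05).
- T = 1.6: 0.05/1.65 = 3.03%
- T = 2.0: 0.05/2.05 = 2.44%

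At T = 1.6 and a 50% deficit, the lesion must fill slightly more than 6% of the region. At exactly 6% the fall is 1.6/0.97 − 1.6 = 0.0495.

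| f·d | Example | Fall at T = 1.6, half / full recovery | Fall at T = 2.0, half / full recovery |
|---|---|---|---|
| 1% | 2% of region, 50% deficit | 0.008 / 0.016 | 0.010 / 0.020 |
| 2.5% | 5%, 50% | 0.021 / 0.041 | 0.026 / 0.051 |
| 5% | 10%, 50% | 0.043 / 0.084 | 0.054 / 0.105 |
| 10% | 10%, 100% | 0.094 / 0.178 | 0.117 / 0.222 |

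**3. Other courses of the lesion.** If it is unchanged, both scans are divided by the same factor and the spurious fall is 0; a real change is only scaled by 1/(1 − f·d), so 0.050 becomes 0.050/0.95 = 0.053 at f·d = 5%. If it worsens, or arises after a reused earlier PET, the denominator drops and SUVR rises: a 3.1% drop (1 − 1.55/1.60) would make a true fall from 1.60 to 1.55 read as no change.

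**4. Positivity.** The denominator loss that lifts T to 1.6 is 1 − T/1.6: 1.3% from 1.58, 3.1% from 1.55, 6.3% from 1.50, 12.5% from 1.40.

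**5. Effect on the group mean.** A spurious 0.05 fall in one patient moves the mean by 0.05/6 = 0.008 to 0.05/5 = 0.010. The individual reading is the more exposed of the two.

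**6. Noise for comparison.** 3% of 1.6 is 0.048. With no true change and normal errors, the chance of a fall above 0.05 in one patient is Φ(−0.05/0.048) = 15% if 3% is the SD of the difference, or Φ(−0.05/0.068) = 23% if it is the SD per scan (0.048 × √2 = 0.068). The chance of at least one such fall is 55% to 73% among five patients and 62% to 79% among six.

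**The case against.** A reader might infer that a cerebellar infarct will by itself produce amyloid positivity or a false tACS response. The documents do not support that. Presence alone produces no fall; uptake in the cerebellum has to rise between the scans, and that is one of three possible directions. No section says that an infarct lowers tracer uptake, that uptake recovers, or how quickly. The in-study interval is short: ten weekday sessions, then follow-up at about one week, although reuse of an earlier PET (B3.A, PET; B6) can lengthen it. At a true SUVR of 1.6 and a 50% deficit, a lesion filling 5% of the region stays below 0.05 even with full recovery. All of this stands. The 5% result is not general, however: at SUVR 2.0 the same lesion gives 0.051.

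On positivity, the true value must lie close below 1.6 unless the lesion is large, and the ratio may not decide alone. The PET section describes a physician's read done as in clinical practice, and the inclusion list accepts an earlier positive scan. That stands too and narrows the positivity part of the point.

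The neurologist's review, and the investigator's freedom to exclude unsuitable patients, make a large evolving lesion less likely to enter. Neither addresses quantification in a patient who is admitted. The cited SUVR methods might define the cerebellar region so as to omit abnormal tissue; that cannot be checked here, and the plan does not say it.

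Finally, measurement error alone produces falls above 0.05 often, and masking leaves that untouched. This is correct and is the larger weakness, but it is no reason to leave a systematic source of error uncontrolled.

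**Conclusion.** The point holds as a gap between the eligibility exception and the SUVR method, which need to be reconciled. If a patient enters under the exception and the lesion evolves, a reference shift of about 3% (3.2% at SUVR 1.6, 2.6% at 2.0) could mimic a 0.05 fall, or hide one if the lesion worsens. A lesion present at baseline could carry a true SUVR just below 1.6 across the threshold.

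It is a conditional risk. It rests on assumed lesion size, uptake deficit and recovery, and on at least one such patient being enrolled; the documents give no number, and it may be zero. At SUVR 1.6, share times deficit must exceed about 3% with full recovery. Lesions of 2% or less of the region at a 50% deficit move a true SUVR of 1.6 by at most 0.016. The case for acting is that the sample is very small, patients are judged individually, there is no control arm, and the remedy is cheap if fixed before results are seen.

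**What to change.** Leave eligibility as it is. Add to Statistical Considerations (B3.B):

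- For any patient admitted under the cerebellar-infarct exception, the infarct identified at the neurologist's review is outlined on the study T1 MRI and removed from the cerebellar reference region. The same mask is applied to both PET scans, for the positivity value and for the change.
- If the baseline MRI was reused from another study (allowed within six months) and predates the lesion, the follow-up MRI is used for the outline. The masked baseline value then comes only after treatment, so it serves as a reported check on positivity.
- Aim 2 is reported with and without such patients.

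The cost is a few sentences, minor image-processing work and slightly fewer reference voxels in affected patients; it is nil if none enrol. The T1 is already combined with PET for targeting (B3.A, MRI). The research MRI has no radiologist read, but the exception itself requires a neurologist to know of the infarct, so no extra reader is needed. The 0.05 threshold still needs separate attention in view of the 3% error.

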**Feasibility and Safety of a High-Frequency Transcranial Alternating Current Stimulation
Intervention for Amyloid- β Reduction in Alzheimer's Disease**

NCT03290326

05/15/2018

PART B STUDY DESCRIPTION

TITLE OF PROTOCOL	Feasibility and Safety of a High-Frequency Transcranial Alternating Current Stimulation Intervention for Amyloid-β Reduction in Alzheimer’s Disease
Principal Investigator	[name]

B1. PURPOSE OF PROTOCOL

Alzheimer’s Disease (AD) is the leading cause of dementia, affecting over 5 million people in the United States alone, and over 30 million worldwide (Hebert, Weuve, Scherr, & Evans, 2013). AD was also the sixth leading cause of death in the US in 2013, and may be a major factor in up to half a million more (James et al., 2014). As the population ages, the prevalence of AD is expected to increase significantly in the future, with estimates suggesting that 7.1 million Americans may suffer from the disease by 2025, as many as 15 million by 2050. Despite this enormous disease burden, therapeutic options are very limited. Specifically, while there are pharmacologic interventions that transiently improve cognitive function, there are no treatments that alter disease progression. As such, the development of a disease-modifying intervention would be of great clinical significance.

The proposed study aims to show that transcranial alternating current stimulation (tACS) is feasible and can be performed in patients with mild AD, and will assess for an initial signal in terms of decreased amyloid, improved neurophysiological markers, and improvement in cognition. In subsequent studies, we will show that this reduction of amyloid is sustained, prevents disease progression, and improves long-term cognitive outcomes. This study will thus provide the critical first step in the development of a novel intervention to prevent and treat Alzheimer’s Disease.

Our central hypothesis is that 10 daily sessions of 40 Hz tACS is safe in patients with mild AD, will significantly decrease cerebral amyloid levels on amyloid PET imaging, and this decrease in amyloid will be correlated with improvement on electrophysiological measures of brain function, and on cognitive testing.

Specific Aim #1: To demonstrate that 10 sessions of 40 Hz tACS stimulation is safe and reliable in patients with mild AD.

We hypothesize that tACS will be well tolerated by all subjects, without any significant side effects.

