The study will be conducted at BIDMC, at the Berenson-Allen Center for Noninvasive Brain Stimulation and in the Clinical Research Center. We aim to study 10 individuals with AD with evidence of increased cerebral amyloid burden on amyloid PET imaging. Up to 20 participants will be enrolled to account for attrition. Each subject's participation in the study will consist of up to 18 visits: 4-5 days for screening/baseline procedures as described below (these baseline assessments may happen over 4-5 days to accommodate scheduling and the participant), 10 tACS study visits, and 4-5 days for follow-up assessments. Subjects will undergo baseline cognitive assessment, structural and functional MRI characterization, resting-state EEG measurement and amyloid PET scan (if not previously obtained). Additionally, patients will undergo a TMS-EEG and a tACS-EEG recording session to assess brain plasticity levels and identify markers of response to stimulation. All subjects will subsequently undergo 10 sessions of gamma-frequency (40 Hz) tACS. The stimulation sites will be identified on a case-by-case basis taking into account the overall distribution of amyloid- β as evidenced by the amyloid PET scan. Subjects will take a standardized adverse effect questionnaire before and after each session to demonstrate safety and tolerability (Fertonani et al., 2015). At the end of the 10 sessions, subjects will then repeat the baseline assessments, followed by repeat amyloid PET imaging to assess for changes in amyloid burden.

Procedures

Screening and Baseline Visit (Visits 1-4)

During the screening and baseline visit, participants will provide informed consent and complete the following procedures:

- Neurological exam*
- Demographic review*
- Review of medical, psychiatric and medication history, including review of diagnosis*
- tACS and TMS safety questionnaires*
- MMSE*
- The Clinical Dementia Rating (CDR) scale to assess severity of dementia*
- Inclusion/Exclusion criteria review*
- MRI screening questionnaire
- Alzheimer's Disease Assessment Scale Cognitive Subscale (ADAS-Cog)
- Baseline Clinical Global Impression of Change (CGIC)

- National Alzheimer's Coordinating Center's Uniform Data Set (NACC-UDS) questionnaires: Activities of Daily Living Inventory (ADL); Geriatric Depression Scale (GDS); Functional Assessment Questionnaire (FAQ)

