If abnormal results are found from the LP, a neurologist on the study in the Berenson-Allen Center will review the results. The neurologist will determine if the finding is in need of clinical follow-up. If this is the case, the neurologist will speak with the participant, will provide a letter describing the findings and need for follow-up and will be available to speak with the participant's provider if they participant agrees and gives permission to do so.

tACS visits (visits 5-14)

Study visits 5-14 will be conducted in the Berenson-Allen Center for Noninvasive Brain Stimulation at BIDMC. Participants will undergo 10 days (weekdays) of tACS. Participants will be allowed to miss one visit for a total of 9 days of tACS. If they miss more than one visit, additional sessions will be added on if it is within a reasonable timeframe as determined by the investigator, in order to reach a total of 9 sessions. Each session will consist of the following:

- Review of tACS side effects and adverse events will be completed daily before and after stimulation. An assessment of any changes in medication or medical history will be assessed on a daily basis.
- Set up for EEG and tACS which includes cleaning the scalp with alcohol, placing a cap with electrodes on the participant's head and applying gel underneath electrodes
- Three minutes of eyes-closed and eyes-open resting state EEG
- 1 hour of 40Hz tACS stimulation to targeted brain regions
 - Additionally, EEG will be recorded throughout the tACS stimulation
- Cognitive assessment (MoCA) will be completed daily to monitor any cognitive changes. If the score drops by 4 points or more, the covering neurologist will be alerted to assess the participant further. The following day, the patients will repeat a MoCA and if the score has not improved they will be reassessed by the neurologist and the participant will not receive stimulation.
- Subjects will be queried each day about their experience and how they are doing. If participants or their family members express that the participant is having difficulty, study staff will work with them to reduce any burden if possible (e.g. arranging reliable transportation, assuring that they have a snack if needed.....).

Follow Up Visit (Visits 15-18)

The following will occur at the follow up visit within approximately 1 week after the completion of the tACS study visits:

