- Cognitive Evaluation that includes the MMSE, NACC-UDS questionnaires and cognitive assessments completed at baseline, RAVLT, ADAS-Cog, and CGIC.
- Repeat baseline UDS questionnaires
- PET Imaging – A follow-up PET scan will be obtained to assess the change in amyloid burden in the stimulated target region
- fMRI
- Lumbar puncture (optional)
- Blood draw
- TMS-EEG plasticity assessment
- tACS-EEG with cognitive tasks
- Adverse event review and follow-up
- Review of medications and changes in medical history
- At the completion of the study, subjects will be queried about their overall experience with the study using the Participant Experience Assessment

It is possible that the follow-up visit will be conducted over 4-5 days due to availability of the PET scanner and resource availability.

If participants have plasticity measures or neuropsychological testing from a prior study in the B-A Center, those may be compared to the measures obtained in this study and/or used in place of the testing in this study.

Telephone Follow-up After (1 month and 3 months after completion of visit 18)

The following will occur via telephone call at two time points, approximately 1 month and 3 months after the participant completes the in-person follow-up visits. for assessment of any longer term changes:

Measures that were collected during prior visits will be completed via telephone:

- Telephone version of MoCA completed with study participant
- CGIC to be completed with study participant and study partner
- Activities of Daily Living Inventory (ADL) –(the number of questions in this may be reduced)

For study participants who already completed the study we plan to complete the telephone follow-up retroactively. If the participant has already passed the 1 month follow-up mark, but not the 3 month mark we plan to call them at two time marks-- immediately and at the 3 month mark. If the participant has already passed both the 1 month and 3 month marks, we plan to complete the follow-up assessment with them at one time mark, following up with them as soon as possible.

Methods

Cognitive Measures

Alzheimer's Disease Assessment Scale (ADAS-Cog):

The ADAS-Cog is a standardized neuropsychological assessment that measures the severity of symptoms of Alzheimer's Disease in 11 different domains. The tasks assess the domains of language, praxis, memory, attention and executive function.

Alzheimer's Disease Cooperative Group Study Clinical Global Impression of Change (CGIC):

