The lumbar puncture will be completed at baseline and then following the tACS intervention if the participant is in agreement. Each LP procedure will take about 2-3 hours, and will be performed by the study Neurologist in the Cognitive Neurology Unit or in the Clinical Research Center. During the LP, participants are placed in a left lateral position, with the back flexed, and knees are drawn up towards the chest. The lumbar region of the back will be cleaned with betadine, twice. Lidocaine 1% will be injected into the subcutaneous area between the L3-4 or L4-5 spinous process. Once the area is numb, an LP needle will be placed and CSF will be collected. To clear any blood from minor trauma associated with needle insertion, the first 1-2 ml of CSF are discarded (or more if needed) to eliminate blood, and then 10-20 ml (2-4 teaspoons) of CSF will be collected. CSF will be processed by the Clinical Research Center laboratory. Approximately half will be sent to LabCorp for processing, and the remainder will be frozen, and later batch-shipped to an outside laboratory for processing or stored for future testing. Participants will be asked to lie flat for 1-1/2 to 2 hours following the LP and given discharge instructions and a phone number to call if they have any concerns. The day after the LP the participants will be contacted by phone to see how they are feeling.

The risks associated with a lumbar puncture are primarily related to the development of a spinal headache. Fortunately, the risk is reduced in the elderly and will be further reduced by the use of a small gauge spinal needle. The benefits for the LP are that it will allow for determination of changes in tau level that cannot be measured in any other way. Given the critical role for tau in Alzheimer's disease, a reduction of the elevated tau levels in the CSF after the intervention would be a strong signal of target engagement and efficacy. The LP will also be used to correlate the presence of amyloid in CSF with the presence displayed on the PET scans. Patients will be informed of the risk/benefit ratio and reminded that it is an optional procedure. Analyses of CSF samples will include multiple markers, such as Abeta42, Abeta40, total tau, phospho-tau181, cytokines, YKL-40, and BDNF. Assays will be performed by the central biomarker laboratory. CSF samples will also be frozen

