TMS-EEG and tACS-EEG analysis. Specifically, the TEPs will be studied using traditionally employed metrics such as the absolute magnitude and time-to-peak of the EEG signal, global mean field amplitude, power in various frequency bands, cortico-cortical coherence in various frequency bands, significant current density, phase-locking, and significant current scattering. Measures including spectral power, coherence and connectivity will be used to assess the impact of tACS on EEG dynamics. ANOVA will be used to determine whether these metrics vary as a function of brain region across subjects. The EEG functional connectivity will be assessed using a variety of different metrics, including cross-correlation coefficient, coherence, synchronization likelihood, transfer entropy, partial directed coherence, and Granger causality. These metrics will be calculated on EEG recorded during the eyes-closed resting state. Values will be obtained for multiple segments of data of various window sizes (generally on the order of 4 to 10 seconds to permit analysis of low-frequency bands) before and after rTMS and tACS; consequently, multiple data segments will be available in each period. Each statistical analysis will be based on a significance threshold equal to $p.0.05$, correction for multiple comparisons will be applied when needed by using Bonferroni correction, False Discovery Rate (FDR) or network-based statistics (NBS).

C. Subject Selection

Subjects will be recruited from BIDMC and outside providers and will have had an amyloid positive PET scan, or suspected amyloid burden.

Inclusion Criteria:

- Clinical Diagnosis of mild AD*
 - Clinical Dementia Rating (CDR) = 0.5 - 1
 - Mini Mental State Examination (MMSE) \geq 20
 - Demonstration or history of memory impairments.

* Confirmation of diagnosis will be made by the study MD based on a holistic consideration of the participant's cognitive evaluation and history.

- Previous amyloid positive PET imaging or suspected to be amyloid positive
- At least 45 years old
- Minimum of completed 8th grade education
- On a stable dose of medications for memory loss including cholinesterase inhibitors (e.g. donepezil, rivastigmine or memantine) as defined as 6 consecutive weeks of treatment at an unchanging dose
- No history of intellectual disability

Exclusion Criteria:

- Current history of poorly controlled migraines including chronic medication for migraine prevention

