Adverse effects will be collected from the start of the experimental protocol to the end of study participation. All adverse events, regardless of attribution to tACS or pre/post assessments, will be collected and recorded using standard adverse event forms. Participants will be asked, in an open-ended way, about the presence of any such events. Also, a standard questionnaire for tACS-related adverse effects will be performed in the period after every tACS session. Intensity of each adverse event will be graded as mild, moderate or severe. Events will be medically evaluated as appropriate, including testing and referral.

General Safety Plan

A licensed physician, credentialed at BIDMC will be available by pager during all tACS and TMS visits at

BIDMC. Furthermore, the person applying tACS and TMS will have training in basic life support (BLS) with the availability of emergency equipment. We will monitor patients in detail during and after delivery of tACS, and TMS using an approach drawn directly from suggested guidelines.

Withdrawal Criteria

Subjects may be withdrawn from the trial if:

- A serious adverse event occurs.
- The investigator considers it, for safety reasons, in the best interest of the subject that he/she be withdrawn.

B6. RECRUITMENT AND CONSENT PROCEDURES

Recruitment

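### Safety is Aim 1 in a memory-impaired sample, yet the plan names no informant source for adverse events, so events between visits may be missed

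*Combined protocol and SAP*

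**What the plan says.** Section B1 gives Specific Aim 1 as: "To demonstrate that 10 sessions of 40 Hz tACS stimulation is safe and reliable in patients with mild AD". The attached hypothesis is that every subject tolerates tACS without notable side effects. The inclusion criteria in B3.C require mild AD (CDR 0.5 to 1, MMSE of at least 20) and "Demonstration or history of memory impairments".

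These safety enquiries name a respondent, and it is always the participant:

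- B5, Adverse Event Monitoring: "Participants will be asked, in an open-ended way, about the presence of any such events".
- B3.A, Study Design: "Subjects will take a standardized adverse effect questionnaire before and after each session to demonstrate safety and tolerability".
- B3.A, tACS visits: "Subjects will be queried each day about their experience and how they are doing".
- B3.A, Lumbar Puncture: "The day after the LP the participants will be contacted by phone to see how they are feeling".

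Others name no respondent. B5 says that "a standard questionnaire for tACS-related adverse effects will be performed in the period after every tACS session". The daily review under tACS visits, the review of adverse reactions in the Data Safety Monitoring Plan and the adverse event review at follow-up are also silent on who answers.

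An informant is used for other measures. Under Methods, the CDR rests on a structured interview of the patient and a family member or caretaker, and the CGIC interviews a family member at baseline and again later. For the 1- and 3-month calls the plan lists "CGIC to be completed with study participant and study partner". Those calls also include the telephone MoCA and the ADL inventory, but no adverse event item.

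**The concern.** The adverse event record is the evidence for the first aim. The review before each session has to pick up what happened since the last one, and that depends on recent recall, which is the faculty impaired in this sample. The plan uses an informant to rate dementia severity and global change but names none for harms.

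Any failure of recall lowers the recorded count and so moves the result towards the hypothesis. All subjects receive active tACS, so there is no control arm in which the same loss would occur and cancel. An event at home that nobody asks about at the time is also hard to recover later.

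**Working it through.** **Step 1: who is asked, and over what interval.**

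- *During treatment.* Sessions run on 10 consecutive weekdays with review before and after each (B3.A). The recall interval is about 1 day, or 3 days from Friday to Monday.
- *After treatment.* The in-person follow-up falls within about 1 week of the last session, and its adverse event review names no respondent.
- *After the in-person follow-up.* The calls come at about 1 and 3 months. Adverse event review is listed for neither, in the text or in the visit schedule. B5 says collection runs to the end of participation, and the plan does not say whether that includes the calls.

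The gap is therefore narrow during treatment and wider afterwards.

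**Step 2: what else could pick up an event.**

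- *Family comments* (B3.A, tACS visits). If relatives say that the participant is struggling, staff try to lessen the burden. The comment is unsolicited, and no link to an adverse event form is stated.
- *Daily MoCA.* It does not depend on anyone reporting an event, and a drop of 4 points alerts a neurologist. It would not show a fall, a headache or a nocturnal event.
- *CGIC interview.* It covers behaviour and functioning with the family member, but produces a rating of change, not an event record.
- *Geriatric Depression Scale.* It is repeated at follow-up and gives some cover for mood.

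**Step 3: how much missed reports could matter.** The plan states no expected event rate or reporting rate, so there is no figure to reproduce. The following is an illustration only. Let n be the number of participants, p the true share with a between-visit event, and s the chance that such an event is reported. The target n is 10 (B3.A, Study Design). Both p and s are assumptions.

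P(no event recorded) = (1 − p·s)^n

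| n = 10 | s = 1 | s = 0.8 | s = 0.5 |
|---|---|---|---|
| p = 10% | 0.90^10 = 0.35 | 0.92^10 = 0.43 | 0.95^10 = 0.60 |
| p = 20% | 0.80^10 = 0.11 | 0.84^10 = 0.17 | 0.90^10 = 0.35 |
| p = 30% | 0.70^10 = 0.03 | 0.76^10 = 0.06 | 0.85^10 = 0.20 |

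If no event is recorded, the one-sided 95% upper bound on the true share solves (1 − p·s)^n = 0.05, so p = (1 − 0.05^(1/n)) / s.

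- n = 10: 1 − 0.05^(1/10) = 0.259, giving 26% at s = 1, 32% at s = 0.8 and 52% at s = 0.5.
- n = 6, the upper end of the 5 or 6 completers expected in B3.B: 1 − 0.05^(1/6) = 0.393, giving 39%, 49% and 79%.

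In a sample this small, a clean record already excludes little, and incomplete reporting weakens it further.

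**The case against.** A reader might infer that adverse events are elicited only from participants. The documents do not support that. Several reviews name no respondent, and B5 says that all events are collected whatever their attribution, with no limit on source. The gap is that no informant is specified; informants are not excluded.

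A reader might also infer that harms between visits are under-counted. The documents support a risk, not that fact. Disease is mild, and during treatment the recall interval is short, with a standardized questionnaire plus a daily check of medication and medical history changes. Many of the tACS effects listed in B5, such as tingling, itching and visual sensations, are subjective, arise during or soon after stimulation, and are asked about on the spot. A partner could not observe them. The daily MoCA and the CGIC interview add some cover. The reporting rates above are assumed and say nothing about this trial.

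All of this stands and narrows the point to events away from the clinic that a partner could notice. It does not remove it: none of these routes asks an informant whether an adverse event occurred. The statement in B6 that mild deficits do not impair understanding of procedures and risks concerns consent, not recall of events.

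Cost is the other fair objection. No partner interview is scheduled on the treatment days or for the call after lumbar puncture, and B3.C does not make a study partner a condition of entry. Asking there goes beyond adding a question for someone already being interviewed.

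**Conclusion.** The point holds as a risk of missed between-visit events, in the direction of the Aim 1 hypothesis. It rests on three features of the text: memory impairment is an entry criterion, the participant is the only respondent named for adverse event questions, and no informant source is specified although one is used for the CDR and CGIC.

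The size is unknown. Under the assumed 20% event share in 10 participants, halving the reporting rate raises the chance of an empty record from 11% to 35%, and the bound from a zero count moves from 26% to 52%. Those figures show how sensitive a sample of 10 would be, not how much is being missed. This is an inexpensive improvement to ascertainment. It does not show that the safety data are invalid.

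**What to change.** In B5, Adverse Event Monitoring, state that the study partner is asked the same open-ended adverse event question as the participant:

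1. at every contact where the partner is already interviewed, namely the follow-up CGIC and the 1- and 3-month calls, with an adverse event item added to those calls for both respondents;
2. at pre-session reviews and at the call on the day after lumbar puncture, when the partner is present or can be reached.

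Record the source of each report (participant, partner or both), and count an event reported by either. Recording the source also allows the participant-reported count to be shown separately.

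The cost is a few minutes per contact. The contacts in item 1 already exist, so they need no extra staff or procedure. Coverage under item 2 will be incomplete, because a partner is not an eligibility requirement and none is scheduled for those visits. The report should say at how many contacts a partner was asked.
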